Address: [name]

[contact]

Study Protocol: **Cerclage After Full-dilatation caesarean-section**

IRAS ID:261294

REC: REC 19/LO/1270

Version 2.0

Date: 10.09.19

Email: [contact]

Name: [name]

Address: [name]

Email: [contact]

Name: [name]

Address: [name]

[contact]

Email: [contact]

Title of clinical trial	An investigation into the role of previous in labour caesarean section in future preterm birth risk and management strategies
Protocol Short Title/Acronym	CRAFT: Cerclage after full dilatation caesarean-section
Study Phase if not mentioned in title	Not applicable
Sponsor name	King's College London and Guy's and St Thomas' Hospital
Chief Investigator	[name], Department of Women and Children's Health, King's College London [name] [contact]
REC number	19/LO/1270
Medical condition or disease under investigation	Increased risk of preterm birth following previous caesarean section in labour
Purpose of clinical trial	
CRAFT-OBS: Observational Study; To evaluate subsequent pregnancy risk of preterm birth in women with a history of previous caesarean in established labour. This prospective study using clinically acquired cervical length and quantitative fetal fibronectin data will help establish a predictive model of preterm birth <34 weeks and <37 weeks.
 
CRAFT-RCT: Randomised controlled trial arm; To assess treatment for short cervix in women at high risk of preterm birth following a caesarean section at fully dilated
 
CRAFT-IMG: Imaging sub-study; To aid understanding of micro and macrostructural features within the cervix which predisposes to preterm birth in women with a previous full dilatation caesarean section. This will use MRI and an advanced transvaginal ultrasound protocol and to assess if structural changes can be visualised in the cervix.

Primary objective	
 1. CRAFT-OBS: To assess the risk of preterm birth or late miscarriage in women following an in labour caesarean section 2. CRAFT-RCT: To assess if cervical cerclage reduces preterm birth in pregnant women with a short cervix following a previous in labour caesarean section 3. CRAFT-IMG: To assess if alterations in MRI parameters or ultrasound characteristics occurs in women who undergo a late miscarriage or preterm birth following an in labour caesarean section.
Trial Design	Prospective observational study, nested randomised controlled trial and imaging sub-study in a selected cohort
Endpoints	Incidence of preterm birth at < 34 weeks gestation
Sample Size	CRAFT-OBS: 2200 women, CRAFT-RCT: 1000 women, CRAFT-IMP: 60 women

Study Protocol: **Cerclage After Full-dilatation caesarean-section**

IRAS ID:261294

REC: REC 19/LO/1270

Version 2.0

Date: 10.09.19

Summary of eligibility criteria	CRAFT-OBS: pregnant women 14 ⁺⁰ -23 ⁺⁶ week with a previous history of caesarean section in labour. CRAFT-RCT: pregnant women with a previous history of caesarean section carried out at full dilatation and a short cervix ($\leq 25\text{mm}$) in current pregnancy. CRAFT-IMG: pregnant women with a previous history of caesarean section carried out at full dilatation (30 women with cervix $>25\text{mm}$; 30 CRAFT-RCT participants).
Maximum duration of treatment of participant	Until delivery or removal of cerclage at 37 weeks gestation
Version and date of final protocol	Version 2.0 (10/09/19)
Version and date of protocol amendments	To be inserted

[figure not shown]

Figure 1: Flow of participants through CRAFT project

STUDY SYNOPSIS.....	4
LAY SUMMARY.....	8
PROFESSIONAL SUMMARY	8
GLOSSARY OF TERMS	11
1. Introduction.....	12
1.1. Background.....	12
1.2. Rationale for study.....	13
Study aims and objectives	15
2.	
2.1. Aims.....	15
2.2. Study objectives	15
2.2.1. CRAFT-OBS: a study of risk and management in women with a history of CS in labour	15
2.2.2. CRAFT-RCT: a trial of USS indicated cerclage in women with history of FDCS	16
2.2.3. CRAFT-IMG: a sub-study evaluating imaging methods for assessing risk and management of women with a history of FDCS.....	16
3. Study Design	16
3.1. CRAFT-OBS.....	16
3.2. CRAFT-RCT	16
3.3. CRAFT-IMG	17
3.4. Expected study duration	17
4. Study Endpoints	17
4.1. CRAFT-OBS.....	17
4.2. CRAFT-RCT	18
4.3. CRAFT-IMG	18
5. Sample size and power calculation	19

There are multiple factors which predispose women to preterm birth such as surgery to the neck of the womb, previous preterm birth and multiple pregnancies. A new factor now found to be contributing to this risk is if the mother has had a previous full dilatation caesarean section (FDCS) in labour particularly when she is 10cm dilated. We don't know how significant this risk is in the UK and the mechanism is not proven but what is known is that it particularly affects pregnancies under 28 weeks and also results in many late miscarriages (14-23⁺⁶ weeks). It is thought it occurs because a cut is made to the cervix (neck of the womb) at the time of the caesarean which weakens it. We do not routinely look for a scar on transvaginal ultrasound when measuring the cervical length (CL).

New NHS Commissioning guidelines(1) and *Saving Babies Lives Care Bundle*(2) has now recommended to screen all women with a previous FDCS because of this new widely reported risk. We don't know whether a cerclage (stitch) inserted into the cervix, first line prophylactic treatment in many UK units for a short cervix (≤ 25 mm), works in this group of women. We have never imaged the cervix looking for injury in this FDCS group of women and compared it to our assessment with routine transvaginal ultrasound. We also do not know if a cut off of ≤ 25 mm is a short cervix in women with a previous FDCS. Furthermore, we do not know how many women with a previous caesarean at 4-9cm dilatation has a risk of preterm birth in the future nor if our current tests of cervical length and fibronectin test work well to predict preterm birth in these women. A cerclage for a short cervix ≤ 25 mm in women with a previous FDCS is not part of routine care. Hence why there is a three-pronged approach in CRAFT:

1. Observational study of women with a previous caesarean in labour
2. A randomised trial of women with a previous FDCS being treated with and without a cerclage if their cervix is short (≤ 25 mm)
3. Imaging sub-study using transvaginal ultrasound and magnetic resonance imaging (MRI) to characterise any scars found to try to work out the mechanism of the problem.

PROFESSIONAL SUMMARY

Study Protocol: **Cerclage After Full-dilatation caesarean-section**

IRAS ID:261294

REC: REC 19/LO/1270

Version 2.0

Date: 10.09.19

Preterm birth (PTB), birth before 37 weeks gestation, has a global prevalence of 9.6% and over a million annual neonatal deaths. Recently, it has been observed FDCS are associated with recurrent, early premature births and late miscarriage (LM). Over 25% of all deliveries in the UK are by caesarean section (CS) and at least one in seven of these occur at full dilatation, affecting 20,000 women per year. These women have a six-fold increased incidence of subsequent preterm birth compared with women who undergo 1st stage CS earlier in labour, which equates to 2500 women per year in the UK. In women who lose a pregnancy, more than half will also go on to experience recurrent pregnancy losses in spite of current intervention. Prediction and management of these cases requires further understanding of its aetiology, assessment of current prediction strategies as well as clinical management.

Despite the emerging association between FDCS and the risk of PTB/LM, the risk following an in labour CS, not at full dilatation, is unknown. It is thought that late stage caesareans, from 7cm onwards, are likely to carry some risk of future preterm birth (3). Furthermore, our current predictive models of preterm birth based on transvaginal ultrasound and quantitative fetal fibronectin are not validated in this specific cohort of women. In this CRAFT study we will evaluate the risk of preterm birth in women with a previous history of caesarean section in labour.

Clinically, a short cervix (≤ 25 mm) on transvaginal ultrasound scan (TVS) during the second trimester identifies women at high risk of PTB/LM. These women may benefit from prophylactic treatment such as a cervical cerclage but currently it is not part of routine care. At present it is unknown whether the ≤ 25 mm cut-off is a reliable predictive measure of risk in women following in labour CS. The mechanism of late miscarriage and early premature births < 34 weeks needs to be further understood with the imaging modalities available to us.

There will be three components to the CRAFT project: 1) CRAFT-OBS 2) CRAFT-RCT and 3) CRAFT-IMG Study

CRAFT-OBS: a study of risk and management in women with a history of CS in labour

We will screen all pregnant women with a history of caesarean section in labour booked for maternity care at all participating sites with transvaginal ultrasound and quantitative fetal fibronectin (if available) between 14⁺⁰ and 23⁺⁶ weeks with a previous in labour CS. These women will be grouped into:

1. Unknown dilatation at time of CS in labour.
2. Dilated 4cm to 9cm at time of CS in labour.
3. Full dilatation at time of CS in labour.

This part of the project will allow us to:

1. Determine pregnancy outcomes in women who have had previous in-labour CS.
2. Evaluate risk of PTB/LM according to degree of dilatation in previous in-labour CS.

Study Protocol: **Cerclage After Full-dilatation caesarean-section**

IRAS ID:261294

REC: REC 19/LO/1270

Version 2.0

Date: 10.09.19

3. Evaluate the predictive value of quantitative fetal fibronectin in women with previous CS in labour if done by direct care team for clinically indicated reasons at any point
4. Evaluate the predictive value of transvaginal ultrasound and whether cervical defects can be identified if performed by direct care team for clinically indicated reasons at any point.
5. Identify women who require referral into specialist preterm surveillance clinics.
6. Identify potential participants for CRAFT-RCT (see Figure 1).

CRAFT-RCT: a trial of USS indicated cerclage in women with history of FDCS

The aim of this trial is to evaluate efficacy of cervical cerclage in pregnant women with a short cervix ($\leq 25\text{mm}$) on TVS between 14⁺⁰ and 23⁺⁶ weeks gestation following a FDCS. The study will allow us to evaluate the impact of cervical cerclage on:

1. Primary obstetric outcome – spontaneous preterm birth rate < 34 weeks gestation.
2. Secondary outcomes - Short-term pregnancy and neonatal outcomes, including a composite of neonatal death and morbidity.

CRAFT-IMG: a study evaluating imaging methods for assessing risk and management of women with a history of FDCS

This imaging sub-study will focus on analysis of TVS and magnetic resonance imaging (MRI) of cervical defects in this population to elucidate which women are at increased risk of PTB/LM. Assessment of any identified cervical defect and its relation to a cervical cerclage will also help us to establish which women at risk of PTB would benefit from this treatment.

Objectives of the imaging study:

1. To assess whether cervical abnormalities can be visualised in the cervix by TVS and MRI.
2. To determine which women in this FDCS cohort are most at risk of preterm birth.
3. To identify which women with a previous CS in established labour are most likely to benefit from a cervical cerclage.

Investigating the mechanism underpinning the increased risk of PTB/LM will aid our understanding of risk in women with a history of FDCS only and inform current and future treatment strategies. We will recruit 30 women with a CL of $> 25\text{mm}$ and 30 women with a CL of $\leq 25\text{mm}$ (short cervix). Women with a short cervix will be participants of the main RCT. Half of these women will have had a cervical cerclage as part of their management.

GLOSSARY OF TERMS

FDCS	Fully dilated caesarean section
CS	Caesarean section
MRI	Magnetic Resonance Imaging
PTB	Preterm Birth
LM	Late miscarriage
TAC	Transabdominal cerclage
CL	Cervical length
qfFN	Quantitative fetal fibronectin

1. Introduction

1.1. Background

Preterm birth (PTB), defined as birth less than 37⁺⁰ weeks gestation, is a significant health issue and is the most important single determinant of adverse infant outcome with regards to survival and quality of life(4). Morbidity is inversely correlated to gestational age, and the most significant adverse outcomes are associated with very preterm birth, defined as occurring less than 32⁺⁰ weeks gestation. Preventative measures which prolong fetal gestation by 1 week, such as those proposed by this study, could save health services £939 million per year in England and Wales(5).

The insertion of a suture around the cervix under regional anaesthesia is an established management strategy in those women at high risk of preterm birth. There is little consensus on the optimal procedure, technique or timing of insertion. Its mechanism of action has been hypothesised as not only supportive but as reinforcing the immunological barrier which protects the fetus from ascending vaginal infection. The benefit of an ultrasound indicated cerclage following evidence of cervical shortening ($\leq 25\text{mm}$) on transvaginal ultrasound scan has been reported to demonstrate a significant reduction in delivery <35 weeks gestation compared with expectant management (6).

The primary risk factor for PTB in multiparous women is a previous PTB(7). Emerging evidence has shown an association between late miscarriage (LM) (14-24 weeks) and PTB in women with a history of full dilatation caesarean section (FDCS) at term, affecting approximately 13.5% of these women. This is hypothesised to be due to a uterine incision, which is inadvertently too low, in or near to effaced cervical tissue. This occurs because the cervix becomes continuous with the lower segment of the uterus at full dilatation and the anatomy can often be distorted. Disruption and scarring of this cervical tissue is thought to result in cervical incompetence in future pregnancies. The association between FDCS and LM/PTB has only recently been recognised and it presents a pressing clinical problem.

Over 25% of all deliveries in the UK are by CS and up to 20% of in labour caesarean sections occur at full dilatation, which could affect up to 20,000 women in the UK per annum (8). These women have a six-fold increased incidence of subsequent preterm birth compared with women who undergo CS in the first stage of labour (adjusted odds ratio 5.8; 95% confidence interval 1.08-30.8)(3); 13.5% in comparison with 2%. This equates to around 2500 women per year in the UK. In women who lose a pregnancy, more than half will also go on to experience recurrent pregnancy losses in spite of intervention, compared to 14% of women with a history of preterm birth without previous FDCS (relative risk 3.06 95% confidence interval 1.22-7.71)(9). The relative risk of PTB in women with a previous emergency CS earlier in labour is unknown, however it is thought to be a continuum of risk, i.e. the later in labour the CS is carried out, the higher the risk of PTB in future pregnancies.

A screening programme to assess for cervical shortening in women with a previous FDSC is due to be implemented as part of new NHS commissioning guidance(1) and the revised *Saving Babies Lives Care Bundle*(2). It is unknown whether transvaginal cervical length screening for a short cervix predicts outcome in this group and there is currently limited evidence to inform optimal management of these women. It is also unknown whether first-line interventions for short cervix $\leq 25\text{mm}$ (vaginally-placed cerclages inserted in the distal cervix during pregnancy), used in other high-risk groups of women, is effective in this cohort. Preliminary data indicates that these interventions may be less efficacious, likely due to the injury having occurred in the proximal cervix, above the cerclage. A small retrospective analysis indicated that of 19 women who had experienced a LM/PTB subsequent to a FDSC and who then had a cerclage in the 3rd pregnancy, 10 (53%) still delivered <30 weeks gestation in comparison with 3% of a high-risk control group, who also had a cervical cerclage in situ after a LM/PTB (n=154).

This study has been developed in collaboration with the Preterm Birth Studies PPI Group at St Thomas' Hospital. They have confirmed that this issue is of vital importance to them and they will be consulted on all study literature and future directions associated with this project.

1.2. Rationale for study

The overall aim of the CRAFT project is to investigate the role of previous in labour caesarean section in future preterm birth risk and management strategies.

[figure not shown]
CRAFT-OBS will determine the risk of spontaneous PTB in women with previous CS in labour. We will use any data on qfFN testing and CL measurements to validate current predictive modelling of preterm birth using these tests, which are the most commonly used predictors of PTB. Participants whose CS was carried out at full dilatation, and whose cervix measures $<25\text{mm}$ will also be invited to take part in the CRAFT-RCT (n=1000) and CRAFT-IMG (n=30). Participants with a history of FDSC and a cervix $\geq 25\text{mm}$ will be offered the opportunity to participate in CRAFT-IMG (n=30).

CRAFT-RCT will determine whether an ultrasound-indicated cervical cerclage is an effective management option in women with cervical shortening following a FDSC. It will also determine if a shortening cervix predicts outcome in this cohort. If it is demonstrated to be ineffective, further research will be required regarding alternative screening and treatment options. This may include imaging the cervix pre-pregnancy for evidence of cervical defects and/or offering a transabdominal cerclage (TAC) in the proximal cervix pre-pregnancy above the level of hypothesised defects.

CRAFT-IMG will inform development of methods for identifying cervical defects in women with a history of CS in labour. We will explore the value of scanning the cervix for scars/areas of abnormality to indicate which women are most at risk of adverse outcomes and require further monitoring and therapy. Currently the ultrasound-assessed CL is the only parameter used in

clinical practice to guide management of women at high risk of PTB and this has not been validated in women with previous FDCS. There is a need to evaluate the features of the cervix and any scar tissue by both MRI and US to evaluate which characteristics can accurately determine which women are likely to go on to experience LM/PTB. Preliminary data indicates that scars can be consistently identified on ultrasound and their location defined in relation to the internal-os of the cervix. MRI can provide additional information regarding tissue microstructure. Previous studies have indicated that changes in signal intensity of cervical stromal layers have been found on T2 weighted images(10) and alterations in basic diffusion imaging (a measure of Brownian motion of water molecules in tissue enabling assessment of microstructure) with relation to the onset of labour reported(11). This will help evaluate the value of imaging and our ability to predict who will need a cerclage – for example location of scar from FDCS.

The development of sophisticated diffusion techniques such as Intravoxel Incoherent Motion (IVIM), has enabled assessment of tissue microstructure, diffusivity and perfusion(12). This separates diffusion perfusion from true diffusion effects, the signal decay is described by a biexponential instead of a mon-exponential equation which yields a more accurate description of the underlying tissue properties(13). This technique has been used to assess perfusion in cervical carcinoma(14) but has not been investigated in relation to PTB. [name] (UCL), a world leading expert in the field of diffusion MR imaging, has previously harnessed these techniques in the assessment of the breast, brain, placenta, and prostate. In this project, his team will facilitate optimal data acquisition and analysis of the cervix using IVIM.

Pilot Data

Figure 1: preliminary data demonstrating the basic quantification of cervix microstructure with MRI. A cervical defect can be seen ex-vivo from a pathology specimen of a uterus and cervix where the patient had previously undergone a full dilatation caesarean section (a). MRI imaging shows a similar cervical defect (b). The left image is T2 weighted and apparent diffusion coefficient (ADC) map and fractional anisotropy (FA) maps, both reflecting tissue structure can be seen in the centre and right images. The cervical defect is indicated with the left arrows. The right arrows

indicate the cervical canal.

Defects in the cervix have already been identified by our research group in non-pregnant women who have undergone LM/PTB following a FDCS using MRI. These lesions are comparable to pathology specimens of women with a similar history (see Figure 1).

Ultrasound is a commonly used modality in obstetrics to quantify the CL. The CS scar can be easily identified in the lower uterine segment or cervical tissue using transvaginal ultrasound examination. Using Doppler ultrasound the internal os is identified relative to the height of the uterine arteries bilaterally as they traverse lateral to the cervix (methodology developed by [name] at University College London Hospitals). The scar defect position has been studied prospectively in women with a previous FDCS who booked at University College London Hospital. Results in 87 women seen over 14 months found a 37% rate of PTB in 8 women whose scar defect was ≥ 5 mm from the internal os or within the cervix itself, compared to 5% of 21 women whose scar defect was > 5 mm above the internal os. We will use the same methodology in this trial and imaging study. We will also analyse inter/intra-observer variation in performing cervical ultrasound assessment and compare it to MRI images.

2. Study aims and objectives

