4.1. CRAFT-OBS

Primary endpoint:

- i) Delivery < 37 completed weeks gestation (powered).

Secondary endpoints

- i) Adverse perinatal outcome, defined as a composite outcome of death (ante-partum/intra-partum stillbirths plus neonatal deaths prior to discharge from neonatal services)
- ii) Delivery <34 weeks gestation.
- iii) Gestation at delivery.
- iv) Late miscarriage (14⁺⁰-23⁺⁶ weeks).
- v) Healthcare use, e.g. appointments, hospital admission, cervical length, cervicovaginal fetal fibronectin levels, interventions.
- vi) Predictive modelling to evaluate the ability of CL and fFN to determine risk of preterm birth <34 and <37 weeks
- vii) Other maternal and fetal morbidities, as per COPOP core outcome set for preterm birth intervention studies(15).

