If we have data from participants in this study of their cervical length and/or quantitative fetal fibronectin we will be able to carry out predictive statistics. This would involve calculating ROC curves for prediction of spontaneous preterm birth for both fibronectin and transvaginal cervical

length measurement as a continuous variable, for delivery <24, <30, <34 and <37 weeks gestation. From the optimal thresholds, predictive statistics will be calculated.

6. Participant inclusion and exclusion criteria

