Participants of the imaging sub-study (CRAFT-IMG) will have a minimum of 1 advanced transvaginal ultrasound and 1 MRI up to a maximum of 3 MRIs and 3 advanced protocol transvaginal ultrasound scans (around 5 minutes longer than a cervical surveillance transvaginal ultrasound). The number carried out depends on the length of the pregnancy and patient’s availability. Where possible these will be co-ordinated with clinical appointments to minimise disruption. Participants will be offered reasonable reimbursement for their travel for these additional appointments.

8. Data analysis

CRAFT-OBS: This study will calculate prediction of preterm birth <37 weeks gestation in women with a previous CS in labour by observing clinical pregnancy outcomes. Where data is available the predictive value based on cervical length and quantitative fetal fibronectin will also be assessed. Results will be presented as both odds ratios and risk differences. Standard predictive statistics will be used for prediction of delivery <34 and <37 weeks gestation.

CRAFT-RCT: CRAFT-RCT: Statistical analysis of results will be undertaken by the research team and [name]. The primary analyses will be by intention to treat. The main outcome is delivery under 34 weeks. Secondary analyses will include secondary endpoints as per section 4.2. Standard predictive statistics will be used for prediction of delivery <34 weeks gestation (cervix ≤ 25 mm will be calculated along with area under the curve). We will also validate our current predictive tools of cervical length and fetal fibronectin in this population. Results will be presented as both odds ratios and risk differences, leading to number needed to treat (NNT) if appropriate, according to CONSORT guidelines. A subgroup analysis will be carried out according to other risk factors for preterm birth other than FDCS.

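### CRAFT-OBS is described as a study of spontaneous preterm birth, but its prediction endpoint and analysis count any delivery, so the tests' sensitivity could be understated

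*Combined protocol and SAP*

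**What the plan says.** Two places give CRAFT-OBS, or its prediction work, a spontaneous outcome:

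- Section 1.2: "CRAFT-OBS will determine the risk of spontaneous PTB in women with previous CS in labour".
- Section 5, last paragraph: the predictive work involves "calculating ROC curves for prediction of spontaneous preterm birth", followed by a list of gestational cut-offs for delivery. This paragraph comes after the CRAFT-IMG sample size, so its link to CRAFT-OBS is by content, not by label.

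The operative sections place no restriction on onset:

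- Section 4.1, primary endpoint: "Delivery < 37 completed weeks gestation (powered".
- Section 4.1, secondary endpoint vi: "Predictive modelling to evaluate the ability of CL and fFN to determine risk of preterm birth <34 and <37 weeks".
- Section 8: preterm birth before 37 weeks will be predicted "in women with a previous CS in labour by observing clinical pregnancy outcomes". The standard predictive statistics are for delivery before 34 and 37 weeks, and results are given as odds ratios and risk differences.

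Section 1.1 defines preterm birth by gestation alone. No section defines spontaneous onset, plans to classify births by onset, or says how provider-initiated births or terminations are counted.

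**The concern.** The proposed mechanism is cervical. Section 1.1 says "Disruption and scarring of this cervical tissue is thought to result in cervical incompetence in future pregnancies". That route leads to spontaneous loss or spontaneous birth. A delivery brought forward for maternal or fetal reasons is not an event that a short cervix or raised fibronectin would be expected to predict. The protocol foresees such births: section 7.4 lists planned preterm delivery among the reasons for removing a cerclage in the RCT.

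Two analysts could follow section 5 or sections 4.1 and 8 and report different accuracy for the same tests in the same women. Under the second reading the tests could look poor in this population for a reason unrelated to how they perform. The comparison by dilatation (aim i and objective 2.2.1 i) is exposed to a lesser degree, on ratio scales.

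**Working it through.** **1. The plan's own figures.** Section 5 gives a 15% rate before 37 weeks and 10% relative accuracy. Assuming a 95% two-sided interval, n = 1.96² × 0.85 / (0.15 × 0.10²) = 2177, which agrees with 2200. At 2200 the interval is 13.5% to 16.5%; the printed upper figure of 15.6% looks like transposed digits. The prediction calculation (1000 women, 100 cases, sensitivity 75%) gives a half-width of 1.96 × √(0.75 × 0.25 / 100) = 8.5 points, consistent with the stated 10.

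**2. Sensitivity under an any-delivery outcome.** Inputs from section 5: sensitivity 75%, specificity 83%, 100 events in 1000 women. Assumptions not in the documents: a share s of events is provider-initiated, and these test positive at the false-positive rate of 17%.

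Measured sensitivity = 0.75 × (1 − s) + 0.17 × s. True positives are 100 times this; false positives are 0.17 × 900 = 153. The single-cut AUC is (sensitivity + specificity) / 2.

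| s | Sensitivity | Specificity | PPV | Single-cut AUC |
|---|---|---|---|---|
| 0 | 75% | 83% | 75/228 = 33% | 0.79 |
| 20% | 0.600 + 0.034 = 63% | 83% | 63.4/216.4 = 29% | 0.73 |
| 40% | 0.450 + 0.068 = 52% | 83% | 51.8/204.8 = 25% | 0.67 |

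The fall in sensitivity is about 12 to 23 points, larger than the 10-point precision that section 5 promises.

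**3. Dilatation contrast.** Take illustrative spontaneous rates of 10% (full dilatation) and 5% (4-9 cm), and add provider-initiated births of 2% or 4% equally to both. All four figures are assumptions.

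| Added | Rates | Risk ratio | Odds ratio | Risk difference |
|---|---|---|---|---|
| 0 | 10% v 5% | 2.0 | 2.1 | 5 points |
| 2% | 12% v 7% | 1.7 | 1.8 | 5 points |
| 4% | 14% v 9% | 1.6 | 1.6 | 5 points |

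If the added births occur only among women without a spontaneous event, the risk difference is 4.9 points (11.8% v 6.9%) or 4.8 points (13.6% v 8.8%). It therefore hardly changes, though it is estimated less precisely: for equal groups the sum of p(1 − p) rises from 0.1375 to 0.171 and 0.202.

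**4. Cost of a spontaneous outcome.** If 20%, 30% or 40% of the 100 planned cases are provider-initiated, 80, 70 or 60 remain. The sensitivity half-width becomes 9.5, 10.1 or 11.0 points. If the powered endpoint itself were changed, an assumed 80-60% spontaneous share of the 15% gives rates of 12-9%. The same formula then needs 2818 to 3885 women.

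**The case against.** The strongest reply is that the all-delivery endpoint is the plan's settled choice and section 1.2 is the outlier. The definition in section 1.1, objective 2.2.1 i, the 15% planning rate, section 4.1 and section 8 all omit any restriction to spontaneous onset. The powered result is one cohort proportion, so it contains no contrast to dilute. This stands: a reader might infer that the primary endpoint or the 2200 is wrong, and the documents do not support that. Reading the all-delivery rate as spontaneous risk would overstate that risk, which is a matter of labelling.

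Section 5 also already names spontaneous birth for the ROC curves and derives the predictive statistics from them. If it is followed, the loss of sensitivity does not arise. This stands too, but it leaves an unresolved choice between section 5 and sections 4.1 vi and 8.

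Four other stronger readings fail:

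- That the 13.5% v 2% in section 1.1 would shrink. The text does not say those rates are spontaneous; if they are all-cause, nothing is left to dilute.
- That an effect at 4-9 cm would be hidden. The cohort has no group below 4 cm, and extra events would raise the absolute rate in the 4-9 cm group. Only ratios against full dilatation, or a gradient within 4-9 cm, could be attenuated.
- That the bias is certainly toward no association. This needs equal provider-initiated rates across groups, which the documents do not establish; otherwise it could go either way.
- That terminations materially inflate the counts. The fetal-abnormality exclusion in section 6.2 covers only the RCT, and late miscarriage is defined by gestation alone, so terminations could be counted. But the protocol never mentions them, and their number against about 330 expected events (0.15 × 2200) is unknown.

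**Conclusion.** The inconsistency is real and nothing elsewhere in the protocol resolves it. Its main consequence is for prediction endpoint vi and the section 8 predictive statistics. Taken literally, they would understate sensitivity (about 63-52% instead of 75%), and with it AUC and PPV, while leaving specificity essentially unchanged. That size rests on an assumed 20-40% provider-initiated share and on those births being unrelated to the tests.

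The effect on the dilatation comparison is smaller and conditional. Odds and risk ratios are attenuated if provider-initiated birth is equally common in the groups, the risk difference hardly changes, and the direction is uncertain if the rates differ. The powered cohort rate survives. This is a worthwhile and inexpensive correction, not a flaw in the main CRAFT-OBS estimate.

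**What to change.** - Keep any delivery before 37 weeks as the powered cohort incidence, state that the 15% rate refers to it, and correct section 1.2 to match. The 2200 then stands.
- Define spontaneous onset (spontaneous labour or membrane rupture) against provider-initiated delivery, and record it for every birth.
- In sections 4.1 vi and 8, align with section 5: use spontaneous late miscarriage or preterm birth as the outcome for the dilatation comparison and all predictive statistics, and report the any-delivery result alongside. State in section 5 that its ROC paragraph covers CRAFT-OBS.
- Count terminations separately from late miscarriage and preterm birth.
- Restate the precision claim for sensitivity in section 5. With an assumed 30-40% provider-initiated share the half-width is about 10-11 points, so the 10-point target may not be met.

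Modelling provider-initiated birth as a competing event is optional. The cost is wording plus one coded field from the maternity records that section 7.3 already has reviewed, with fewer events and wider intervals in the spontaneous-onset analyses.
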